Part B will collect long-term safety and efficacy data for an additional 48 weeks. Patients who complete Part A through Week 24 and, in the opinion of the investigator are compliant with treatment, may select to continue the treatment to which they were randomized. If one dosing regimen is determined to be superior either from an efficacy or safety standpoint, Part B may be converted to a single dose regimen and all patients who select to continue or start Part B at that point will be dosed with the selected regimen.

Study duration is up to 80 weeks for patients that complete both Part A and Part B of the study. If patients discontinue study treatment prior to Week 72 for any reason, they should return to the site for an Early Termination visit. All patients who complete the regular study visits through Week 72 in Part B will return for a Follow-up visit 28 days after their End of Study visit.

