5.4. Protocol Deviations

Protocol deviations will be collected and will be categorized as:

- Informed Consent
- Enrollment Criteria
- Dosing
- Concomitant Medications
- Visits/Procedures Required
- Visit Schedule
- Non-compliance
- Regulatory
- Laboratory
- Other

They will also be graded as Major or Minor.

This document is confidential.

SAP Version: 3.0 (15JUL2021)
Controlled Document ID: **3903A.01**, Effective Date 29-Oct-2018
Filing requirements: TMF

Page 20 of 52

Statistical Analysis PlanSponsor: Avalyn Pharma, Inc.; Protocol No.: AP01-002

Major protocol deviations are defined as a subset of protocol deviations that may significantly impact the completeness, accuracy, and/or reliability of the study data or that may significantly affect the subject's rights, safety or well-being. Major protocol deviations will be included in the Clinical Study Report (CSR). These include: Enrollment Criteria (violation of inclusion/exclusion criteria, Informed Consent (informed consent not provided), Dosing (study drug deviation), Non-compliance, Concomitant Medications (administration of prohibit medication) and Other Good Clinical Practice (GCP) deviations. All protocol deviations will be tracked and corrective live actions implemented.

Protocol deviations will be summarized by grade and category for each treatment group and overall in the following ways:

- Patients with Any Protocol Deviations (Major or Minor)
- Patients with Major Deviations Only
- Patients with Minor Deviations Only (i.e. excluding those patients with Major deviations).
- Protocol Deviations Attributable to COVID-19

All protocol deviations will be listed.

This document is confidential.

SAP Version: 3.0 (15JUL2021)
Controlled Document ID: **3903A.01**, Effective Date 29-Oct-2018
Filing requirements: TMF

Page 21 of 52

Statistical Analysis PlanSponsor: Avalyn Pharma, Inc.; Protocol No.: AP01-002

6. General Aspects for Statistical Analysis**6.1. General Methods**

Unless otherwise specified, all data will be summarized by treatment group and overall. A separate summary of data from Part A of will be provided in addition to a full study summary including both Part A and Part B data. Categorical data will be summarized as number and percent of total. Continuous data will be summarized using mean, median, SD and range. Dose response will be evaluated by comparing safety and changes in efficacy variables across the dose regimens.

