All relevant patient data will be included in listings. All patients entered into the database will be included in patient data listings.

Pulmonary function tests (PFTs) (including D_{LCO}) are performed at each study visit.

The following PFTs will be performed at all visits (including Screening) using spirometry (and documented on the PFT eCRF form):

- FVC Liters (L)
- FEV₁ Liters (L)
- % Predicated FVC
- % Predicted FEV₁.

Pre-dose and post-dose spirometry will be performed at the Baseline visit.

At every visit, D_{LCO} ($\text{mL}/\text{min}^{-1}/\text{mmHg}^{-1}$) and % Predicted D_{LCO} will be obtained using the site's standard methodology.

FEV₁/FVC ratio will be derived as: $100 \times \text{FEV}_1/\text{FVC}$.

For comparisons to baseline, data from Visit 2 prior to the first dose of study drug will be used as baseline, unless otherwise noted. For PFTs, the pre-dose result will be used as baseline. Subgroup analyses will be performed based on baseline groupings for FVC, region, age, sex, D_{LCO} and progression-related biomarkers (CXCL13, CCL18, MMP3).

If either regimen is eliminated based on Part A outcomes, patients may be switched to the selected regimen for the remainder of their participation. Data summaries will be created to mimic this switch by using the following treatment grouping for Part B: (1) randomized to 100 mg twice daily; (2) randomized to 50 mg once daily and stayed on 50 mg once daily; (3) randomized to 50 mg once daily and switched to 100 mg twice daily; (4) randomized to 50 mg once daily total [groups 2 and 3 combined]; (5) overall total for Part B data. Descriptive within-patient analyses will be included for those patients who switch from 50 mg once daily to 100 mg twice daily. These analyses will include spider plots of change from baseline showing when the dose switch took place. Data listings will include a variable to denote the regimen switch and flag the time of the switch for affected patients.

No formal hypothesis tests are planned.

This document is confidential.

SAP Version: 3.0 (15JUL2021)
Controlled Document ID: **3903A.01**, Effective Date 29-Oct-2018
Filing requirements: TMF

Page 22 of 52

Statistical Analysis PlanSponsor: Avalyn Pharma, Inc.; Protocol No.: AP01-002

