6.3. Missing Data

Missing values will not be imputed for data displayed in summary tables. For imputation of missing data used for the sensitivity analysis of the primary efficacy variable see Section 8.1.

Completely missing or partial dates will be presented in the listings as reported on CRFs.

If an AE has a completely missing onset date, then the AE will be considered a treatment emergent adverse event (TEAE). A medication with a completely missing start date is considered a prior medication. A medication with a completely missing stop date is considered a concomitant medication.

This document is confidential.

SAP Version: 3.0 (15JUL2021)
Controlled Document ID: **3903A.01**, Effective Date 29-Oct-2018
Filing requirements: TMF

Page 23 of 52

Statistical Analysis Plan

Sponsor: Avalyn Pharma, Inc.; Protocol No.: AP01-002

If an adverse event or a medication has a partial missing start or stop date, the following rules will be used to impute the date; then the imputed date will be used to determine whether it is a TEAE for adverse event, or a prior or concomitant medication.

Table 6: Partial Date Derivation

Partial Missing Start or Stop Date	Derived Start Date	Derived Stop Date
Missing month and day, and the year is present	January 1 of that year or first dose date if the year is the same as the year of first dose date	December 31 of that year
Missing day, but year and month are present	First day of that month or first dose date if the year and month are the same as the year and month of first dose date	Last day of that month
Missing month, but year and day are present	Missing month derived as January or same as first dose month if the year is the same as the year of first dose	Missing month derived as December

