6.4. Visit Windows

All data collected during study follow-up will be displayed and analyzed according to the actual visit data in the eCRF with the exception of early termination visits. Early termination visits will be mapped to the closest study visit, or analyzed according to the actual visit date, when possible.

The study assessments are summarized in Table 1 and Table 2 of the clinical study protocol. All information required by the protocol must be recorded on the source documents. The study schedule must be followed. However, under special conditions (e.g., holidays, weekends), a window of +/- 3 days is permissible for study procedures as long as the proper order of procedures and assessments is maintained. In Phase 2, a window of +/- 7 days is permissible. These windows are not applicable during the baseline period. Out-of-window data will be retained in the tables, listings, and figures. For the Part A interim analysis, Visit 8 will include data collected up to 36 weeks for HRCT and 28 weeks for all other variables.

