The following statistics for in-clinic FVC and FVC % Predicted will be calculated and summarized by treatment group and displayed in a table:

- Summary statistics of in-clinic FVC and FVC % Predicted at Baseline and at each post-Baseline time point (Week 4, 8, 12, 16, 20, 24, 36, 48, 60, 72 and Follow-Up)
- Summary statistics of in-clinic FVC and FVC % Predicted reflecting the absolute change from Baseline to each post-Baseline time point (Week 4, 8, 12, 16, 20, 24, 36, 48, 60, 72 and Follow-Up).

The following plot will be produced for in-clinic FVC and FVC % Predicted:

- Mean FVC (or FVC % Predicted) Change from Baseline (\pm SD) vs. Visit Week (Week 4, Week 8, Week 12, etc.) with lines for each treatment group.

Linear mixed-effects models (PROC MIXED) will be used for the analyses. The model will include the change from baseline in in-clinic FVC (or FVC % Predicted) (measured at any time in the study) as the dependent variable and will include patient and time (continuous) as random effects, fixed effect of time and time-varying effects for treatment group and treatment-by-time interaction to account for those patients who switched dosing regimens from 50 mg once daily to 100 mg twice daily in Part B. Longitudinal plots at selected timepoints displaying the model adjusted, least square means and 95% confidence intervals will be produced.

All in-clinic pulmonary function data will be presented in a listing.

8.2. Secondary Efficacy Endpoint(s) and Analyses**8.2.1. Change from baseline in cough frequency as measured by LCM**

The LCM⁴ is an audio-based cough detection device that allows sounds to be reconstructed and measured as cough events. Patients that pass all of the screening criteria and will be randomized in the study will be provided with a cough monitor to wear for a 24-hour period prior to coming in for their Baseline visit. This will be used as their baseline reading. The LCM and mailing materials will also be dispensed at Visits 5 and 8. Patients will wear for a 24-hour period, fill out the cough monitor paper diary

This document is confidential.

SAP Version: 3.0 (15JUL2021)
Controlled Document ID: **3903A.01**, Effective Date 29-Oct-2018
Filing requirements: TMF

Page 32 of 52

Statistical Analysis PlanSponsor: Avalyn Pharma, Inc.; Protocol No.: AP01-002

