8.2.4. Change from baseline in cough severity as measured by VAS

The European Respiratory Society Cough Severity VAS⁶ will be completed at Baseline, all subsequent visits and the Follow-up visit. This is a paper-based scale that will be completed by the patient at the relevant visits. The scale will range on a vertical line from 'No Cough' at the bottom to 'Worst Cough Ever' at the top. The patient will put a cross on the line to indicate the severity of their cough in the last 2 weeks. The results of the scale will be measured in millimeters from the bottom of the scale to the marked cross and entered into the appropriate eCRF. Appendix Section 14.1 presents an example of the Cough Severity VAS.

The following statistics for Cough VAS will be calculated and summarized by treatment group and presented in a table:

- Summary statistics of the Cough Severity VAS score at Baseline and at each post-Baseline time point (Week 4, 8, 12, 16, 20, 24, 36, 48, 60, 72 and Follow-Up)
- Summary statistics of the Cough Severity VAS score reflecting the absolute change from Baseline to each post-Baseline time point (Week 4, 8, 12, 16, 20, 24, 36, 48, 60, 72 and Follow-Up).

The following plot will be produced for the Cough Severity VAS:

- Mean Cough Severity VAS Change from Baseline (\pm SD) vs. Visit Week (Week 4, 8, 12, 16, 20, 24, 36, 48, 60, 72 and Follow-Up) with lines for each treatment group.

All Cough Severity VAS score data will be presented in a listing.

8.2.5. Change from baseline in extent of fibrosis and lung volumes as assessed by HRCT

HRCT scans will be obtained to measure the extent of fibrosis and lung volumes at the Baseline visit and the Week 24 visit, or at an early termination visit if the patient does not complete Part A. These scans will be read and interpreted by a central reader.

The following statistics from the HRCT scans will be calculated and summarized by lung region and treatment group and displayed in a table:

- Summary statistics of the extent of fibrosis and lung volumes as assessed by HRCT at Baseline and the Week 24 post-Baseline time point, or separately for early terminations at the post-Baseline time point available.
- Summary statistics of the extent of fibrosis and lung volumes as assessed by HRCT reflecting the absolute change from Baseline to the Week 24 time point, or separately for early terminations at post-Baseline time point available.

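### By-visit tables and plots run from Week 4 to Week 72 on observed cases, but only selected patients continue after Week 24, so the Week 24 to 36 step can partly reflect who left

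*SAP*

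**What the plan says.** Entry to Part B is decided after randomisation. SAP 3.3 states: "Patients who complete Part A through Week 24 and, in the opinion of the investigator are compliant with treatment, may select to continue". Protocol 4.1 and the synopsis say the same in substance. Protocol 5.6 also lets the investigator withdraw a patient during Part A for lack of efficacy shown by a marked fall in FVC. Protocol 5.3 requires discontinuation if oral pirfenidone or nintedanib is needed in Part A.

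The by-visit outputs continue across that selection point. SAP 8.1 plans FVC statistics "reflecting the absolute change from Baseline to each post-Baseline time point (Week 4, 8, 12, 16, 20, 24, 36, 48, 60, 72 and Follow-Up", and a mean-change plot by visit ("Week 4, Week 8, Week 12, etc.) with lines for each treatment group"). The same pattern is planned for K-BILD (8.2.2), LCQ (8.2.3), cough VAS (8.2.4: "Summary statistics of the Cough Severity VAS score reflecting the absolute change from Baseline to each post-Baseline time point"), DLCO (8.2.6), CA19-9/CA-125 (9.4), SaO2 (10.5) and FEV1/FVC (10.7).

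The tables use observed cases. SAP 6.3 says: "Missing values will not be imputed for data displayed in summary tables". The imputation for terminated patients in SAP 8.1 serves only the Week 24 FVC sensitivity analyses.

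For patients who leave, SAP 6.4 adds: "Early termination visits will be mapped to the closest study visit, or analyzed according to the actual visit date, when possible".

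SAP 6.1 plans a separate Part A summary "in addition to a full study summary including both Part A and Part B data". For Part B it splits the 50 mg once daily arm into those who stayed and those who switched, and then adds "4) randomized to 50 mg once daily total [groups 2 and 3 combined]; (5) overall total for Part B data". It also plans spider plots for patients who switch from 50 mg once daily to 100 mg twice daily.

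**The concern.** Patients with a Week 24 value who do not enter Part B count at Week 24 and are absent at Week 36. If they were doing worse at Week 24, the group mean rises when they drop out, even if no remaining patient has improved. A reader following the plotted line would see slower decline, or even recovery, and could credit it to longer treatment. If the two arms continue at different rates, or lose different kinds of patient, the between-arm picture after Week 24 shifts as well.

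This matters because Part B exists to gather long-term safety and efficacy data, and the trial has no control group. Readers will look at these lines, above all where a line is the only planned longitudinal group output. The plan has no group-level display that puts Part B entrants' own Part A course next to their Part B course. This applies to the 100 mg twice daily arm too.

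**Working it through.** **The plan's own figure.** SAP 3.5 gives a 95% confidence half-width of 1.25 for mean FVC change with SD 4.5 and 50 per group. Check: 1.96 × 4.5 / √50 = 1.247. It reproduces, and nothing below contradicts a stated figure.

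**The identity.** Let d be the share of patients with a Week 24 value but no Week 36 value. Let gap be the mean Week 24 change in continuers minus that in leavers. Assume everyone seen at Week 36 was also seen at Week 24. Then:

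- displayed step = mean at Week 36 (continuers) − mean at Week 24 (everyone seen)
- = [continuers' own Week 24 to 36 change] + [continuers' Week 24 mean − everyone's Week 24 mean]
- = continuers' own change + d × gap

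**Expected 12-week change, for scale.** SAP 3.5 cites losses at Week 26 of 1.5 points (oral pirfenidone) and 3.9 points (placebo). Over 12 weeks:

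- oral pirfenidone rate: 1.5 × 12/26 = 0.69
- placebo rate: 3.9 × 12/26 = 1.80

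**Size of d × gap in FVC % predicted points.** The documents give neither input, so both are assumed.

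| Share leaving (d) | gap 0 | gap 2 | gap 6 |
|---|---|---|---|
| 5% | 0 | 0.10 | 0.30 |
| 10% | 0 | 0.20 | 0.60 |
| 20% | 0 | 0.40 | 1.20 |
| 30% | 0 | 0.60 | 1.80 |

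**Check by simulation.** Linear decline averaging 1.5/26 points per week, SD 4.5 at Week 24, and leaving dependent on the observed Week 24 change. The true 12-week step is −0.70.

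| d | gap | d × gap | Continuers' own change | Displayed step |
|---|---|---|---|---|
| 10% | about 0 | 0.00 | −0.69 | −0.69 |
| 10% | 2.20 | 0.22 | −0.66 | −0.44 |
| 20% | 2.13 | 0.43 | −0.62 | −0.19 |
| 20% | 3.90 | 0.78 | −0.55 | +0.23 |

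In the last row a group that is still losing function appears to improve. The continuers' own change (−0.55) also differs from the true step (−0.70). An entrants-only display removes the composition term but does not make entrants representative.

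**Which outputs have a model beside the descriptive series.**

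- FVC (SAP 8.1), DLCO (8.2.6) and CA19-9/CA-125 (9.4): a mixed model using visits through Week 72, with least-squares-mean plots.
- K-BILD, LCQ, cough VAS, SaO2 and FEV1/FVC: none.
- Cough monitor and HRCT data stop at Week 24 and are not affected.

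**The case against.** The strongest reply is that the illustration uses FVC, the endpoint that the SAP protects best. If leaving depends on the observed Week 24 value, the data are missing at random and a likelihood-based mixed model largely corrects for it. A simulation with a linear random-slope model (the variance split and linearity are assumptions) and a true step of −0.75 bears this out. With 80% entering and the odds of entry doubling per SD of better Week 24 change, the raw step was −0.14 and the model step −0.76. With 70% entering and an odds ratio of 3, they were +0.55 and −0.74. This stands. A reader might infer that the long-term modelled FVC result is distorted to the extent shown above. The documents do not support that, because the figures describe the descriptive plot.

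Other stronger readings also fail:

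- A reader might infer that nothing shows Part B entrants' Part A course. The spider plots in SAP 6.1 do so for individual switchers. The gap is at group level and for everyone who did not switch.
- A reader might infer that each arm has a single unbroken series only. SAP 6.1 plans a separate Part A summary and splits the 50 mg once daily arm in Part B by switch status. Neither lines up entrants' Week 24 and Week 36 values.
- A reader might infer that everyone who fails to complete Part A feeds the step. A patient who left earlier has no Week 24 value, and counts only if the termination visit is mapped there under SAP 6.4.
- A reader might infer that selection is certain. The investigator's judgement for entry concerns compliance rather than response. Nintedanib is allowed in Part B, so decliners have less reason to leave at Week 24. The term may be zero.
- A reader might infer that the main efficacy result is affected. The primary efficacy endpoint is at Week 24, and the study's primary objective is safety and tolerability.

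Some of the remedy is already planned: counts with data at each visit for K-BILD, LCQ, SaO2 and FEV1/FVC, disposition by part with reasons (7.1), and baseline characteristics for Parts A and B (7.2, 7.4). None of these shows how entrants and non-entrants stood at Week 24.

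**Conclusion.** The point holds for the descriptive by-visit tables and mean plots. Their Week 24 to 36 step mixes the continuing patients' own change with a change in who is measured, and no planned group-level output separates the two. For FVC % predicted the composition part is zero if leavers do not differ. It is about 0.2 to 1.2 points with 10-20% leaving and leavers 2-6 points worse, so it can match or exceed the expected 12-week loss of about 0.7 at the oral pirfenidone rate. The leaving rate, the gap and its direction are assumptions.

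The consequence is smaller for FVC, DLCO and CA19-9/CA-125, whose mixed models reduce the problem if leaving depends on observed values. It is greatest for K-BILD, LCQ and cough VAS, and for the safety summaries of SaO2 and FEV1/FVC, where the observed-case series is the only planned longitudinal group output. The FVC sizes do not carry over to those scales; only the identity does. The same step also carries the regimen switch and any nintedanib added in Part B, which an entrants-only display does not remove.

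**What to change.** Amend SAP 6.1 and at least 8.2.2 to 8.2.4, 10.5 and 10.7, and apply the same to the descriptive FVC, DLCO and CA19-9/CA-125 plots (8.1, 8.2.6, 9.4):

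- Break the plotted line at Week 24.
- Show N at each visit where it is not already planned.
- Add a series for Part B entrants only, by randomised arm and with the SAP 6.1 switch grouping, that includes their own Baseline to Week 24 values.
- Tabulate Week 24 change from baseline for entrants beside non-entrants, by arm.
- State that entrants remain a selected group, and that the modelled estimates are the main long-term results for FVC and DLCO.

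The cost is SAP wording and some extra tables and figures from existing data. With eight endpoint families and several Part B groupings this is more than one added column. If outputs must be limited, start with the five endpoint families that have no model. No visit, assessment or treatment rule changes.

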## Study Duration

This study has two parts. In Part A, each patient will be screened and those enrolled will then receive 24 weeks treatment with AP01. Patients that complete Part A and in the opinion of the investigator are compliant with study procedures will be allowed to continue to Part B of the study for 48 weeks additional treatment.

If patients discontinue study treatment prior to Week 72 for any reason, they should return to the site for an Early Termination visit. All patients who complete the regular study visits through Part B will return for a Follow-up visit 28 days after their End of Study visit (EOS/Visit 12) unless the patient has consented to enroll in the Rollover study, AP01-005.

The end of study for patients that plan to participate in the Rollover study (AP01-005) will be their last treatment visit (EOS/Visit 12) or an safety monitoring visit after Visit 12. The end of the study for patients not enrolling in AP01-005 will be the day of their last Follow-up or Early Termination visit.

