Study duration is up to 80 weeks for patients that complete both Part A and Part B of the study and up to 92 weeks for patients that plan to continue AP01 on the AP01-005 Rollover study. If patients discontinue study treatment prior to Week 72 for any reason, they should return to the site for an Early Termination visit. All patients who complete the regular study visits through Week 72 in Part B will return for a Follow-up visit 28 days after their End of Study visit unless the patient plans to participate in AP01-005. Patients planning to enroll in AP01-005 will continue administering AP01 using EOS/Visit 12 as their Baseline visit for AP01-005. If Regulatory approval for AP01-005 has not been achieved by the time a patient is ready to enroll in AP01-005, the patient will continue treatment that they are receiving at Visit 12 on this study and then transition to the Rollover study upon approval of AP01-005 at their site. Patients will have a visit to assess safety and compliance at least every 3 months while awaiting approval of AP01-005 at their site. The end of the study for all patients will be the day of their last Follow-up or Early Termination visit or their last treatment visit for those enrolling in AP01-005.

Avalyn Pharma, Inc.  
AP01-002

Protocol v2.1  

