#### **6.2.11 Follow-up Visit for Patients NOT Enrolling in AP01-005 (28 days +/- 7 days after the Visit 12 - End of Study visit)**

Follow-up visits will occur 28 days after the End of Study visit for Part B. The following procedures will be conducted in chronological order:

- Cough VAS, KBILD Questionnaire and LCQ
- AEs and concomitant medications since previous visit
- Modified PE (Lungs and CV body systems only)
- Vital signs
- SaO2
- Spirometry and DLCO
- Blood samples for laboratory tests (Chemistry including AST and ALT, Hematology, Biomarkers (CA19-9 and CA-125 only))
- Urinalysis
- End of Study form completion

Patients may experience AEs that necessitate an unscheduled visit. There may also be situations in which the investigator asks a patient to report for an unscheduled visit following the report of an AE or a significant decrease in FVC during home spirometry readings. Additional examinations may be conducted at these visits as necessary to ensure the safety and well-being of patients during the study. Electronic case report forms (eCRFs) should be completed for each unscheduled visit.

Avalyn Pharma, Inc.  
AP01-002

Protocol V2.1  

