**Notes for Tables 5 and 6:**

1. Follow-up visit will occur 28 days after the End of Study visit in Part B of the study.
2. A complete physical exam will be performed at Screening and Baseline visits. A modified physical exam including the patient's lungs and cardiovascular body systems will be performed at all other visits. For Safety Visits, only chest and skin exam are required.
3. Height is collected at the Screening visit only.
4. Blood samples for laboratory tests include: Chemistry (including AST and ALT), Hematology and Biomarkers (Blood samples for biomarkers will not be collected at Screening.) For Safety Visits, only AST and ALT are required.
5. Females of childbearing potential are required to take a urinary pregnancy test at each visit except the Follow-up visit.
6. Patients that pass screening and are scheduled to be randomized will receive a LCM to be worn for 24 hours and returned to the site at the Baseline visit. LCM will be worn for 24 hours at Visits 5 and 8. A paper diary will also be dispensed to the patient to record activities during the 24-hour period.
7. HRCT scans will be performed at Visits 2 and 8. The Baseline HRCT may be skipped if the HRCT for eligibility was performed less than 1 month prior to the Baseline visit.
8. Study material dispensation will occur at Visit 8 for those patients participating in Part B of the study.
9. Patients will be assessed for eligibility to participate in AP01-005 at EOS/Visit 12. Those enrolling in AP01-005 will use EOS/Visit 12 as their AP01-005 Baseline visit.
10. Patients enrolling in AP01-005 will not participate in the Follow-up visit.
11. Patients awaiting site approval of AP01-005 only.

Avalyn Pharma, Inc.  
AP01-002

Protocol V2.1  

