End of Treatment/Study Form				X	X

Notes for Tables 3 and 4:

1. Follow-up visit will occur 28 days after the End of Study visit in Part B of the study.
2. A complete physical exam will be performed at Screening and Baseline visits. A modified physical exam including the patient's lungs and cardiovascular body systems will be performed at all other visits.
3. Height is collected at the Screening visit only.
4. Blood samples for laboratory tests include: Chemistry (including AST and ALT), Hematology and Biomarkers (Blood samples for biomarkers will not be collected at Screening.)
5. Females of childbearing potential are required to take a urinary pregnancy test at each visit except the Follow-up visit.
6. Patients that pass screening and are scheduled to be randomized will receive a LCM to be worn for 24 hours and returned to the site at the Baseline visit. LCM will be worn for 24 hours at Visits 5 and 8. A paper diary will also be dispensed to the patient to record activities during the 24-hour period.
7. HRCT scans will be performed at Visits 2 and 8. The Baseline HRCT may be skipped if the HRCT for eligibility was performed less than 1 month prior to the Baseline visit.
8. Study material dispensation will occur at Visit 8 for those patients participating in Part B of the study.

Table 5 Patient At-Home Assessments

DAILY: Patients will administer AP01 50 once daily or 100 mg twice daily
WEEKLY: Patients will perform home spirometry readings on the same day each week at approximately the same time of day (+/- 2 hours)

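### The SAP has every Week 72 completer attend Follow-up, but protocol v2.1 exempts patients rolling over to AP01-005, so the step from Week 72 to Follow-Up mixes stopping drug with a change in who is measured

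*SAP*

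**What the plan says.** **Who attends.** SAP v3.0 (15 July 2021), section 3.3, gives the rule with no exception: "All patients who complete the regular study visits through Week 72 in Part B will return for a Follow-up visit" 28 days after Visit 12. Note 1 under SAP Tables 3 and 4 repeats it ("Follow-up visit will occur 28 days after the End of Study visit in Part B of the study"), and so does SAP 3.8.2. The readable SAP text does not mention AP01-005. SAP section 12 lists one change from the protocol, the added Full Analysis Set.

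Protocol v2.1 (12 October 2020) differs in four places:
- Synopsis, Study Duration: completers return "unless the patient has consented to enroll in the Rollover study, AP01-005".
- Section 4.1: completers "will return for a Follow-up visit 28 days after their End of Study visit unless the patient plans to participate in AP01-005".
- Section 6.2.11 is headed "Follow-up Visit for Patients NOT Enrolling in AP01-005".
- Note 10 to Tables 5 and 6: "Patients enrolling in AP01-005 will not participate in the Follow-up visit".

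Section 4.1 also says that patients planning to roll over keep taking AP01 after Visit 12.

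**How Follow-Up is analysed.** For FVC, SAP 8.1 tabulates summary statistics "reflecting the absolute change from Baseline to each post-Baseline time point (Week 4, 8, 12, 16, 20, 24, 36, 48, 60, 72 and Follow-Up". The same list of time points is used for K-BILD, LCQ, cough VAS, DLCO, CA19-9/CA-125, SaO2 and FEV1/FVC. Follow-Up is named on the mean-change line plots for K-BILD, LCQ, cough VAS, SaO2 and FEV1/FVC. SAP 6.3 rules out imputation in summary tables. The longitudinal models for FVC (8.1) and DLCO (8.2.6) accept measurements from any point in the study.

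**The concern.** A reader of the SAP would take the Follow-Up column to be the same completers as Week 72, seen 28 days later. Under the protocol it is a subset, and a particular one: every completer measured at Follow-Up has stopped AP01, and every completer who continues AP01 is absent. The change in who is measured coincides exactly with the change in treatment status, so the step between the two columns cannot be attributed to either. Subtracting each patient's own baseline does not help, because the set of patients being averaged still changes.

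The trial has no untreated control. A movement in mean FVC, cough or quality of life just after treatment ends is therefore easy to over-read, in either direction. In the FVC and DLCO models, off-drug values could also be counted under a treatment group, since the treatment term is described only as following the regimen switch and no off-drug state is defined.

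**Working it through.** **1. Is there a real conflict?** The four protocol passages word the condition slightly differently (consented, plans, enrolling), but all remove rollover patients from the visit. The opening of protocol section 6.2 mentions Follow-up without the exception, as a one-line summary; the explicit passages govern. No SAP passage restores the exception or declares a departure.

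The SAP text looks carried over from an older protocol:
- SAP 3.8.2 points to protocol sections 6.2.1 to 6.2.10, but in v2.1 the Follow-up visit is 6.2.11.
- SAP 6.4 cites protocol Tables 1 and 2 for the assessments, which in v2.1 are Tables 5 and 6.
- The dose switch was brought into the SAP; the rollover exception was not.

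**2. Size of the composition effect.** No stated figure is in dispute. Let f be the share of completers who roll over, S the mean Week 72 change among those who do not, and R the mean among those who do. Assume each completer either rolls over or attends Follow-up, with no missing values, and that nobody changes after Week 72.
- Week 72 mean, all completers: (1 - f) x S + f x R
- Follow-Up mean, attenders only: S
- Apparent step: S - [(1 - f) x S + f x R] = f x (S - R)

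The documents give neither f nor S - R. As assumptions, take f from 0.25 to 0.90 and S - R from -4.5 to +2.25 points of FVC % predicted. That is -1 to +0.5 times the SD of 4.5, which the SAP takes from Week 26 of the oral pirfenidone phase 3 trial.

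| f | S - R = -4.5 | -2.25 | 0 | +2.25 |
|---|---|---|---|---|
| 0.25 | -1.1 | -0.6 | 0 | +0.6 |
| 0.50 | -2.25 | -1.1 | 0 | +1.1 |
| 0.75 | -3.4 | -1.7 | 0 | +1.7 |
| 0.90 | -4.05 | -2.0 | 0 | +2.0 |

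For scale, the plan's 95% CI half-width of 1.25 reproduces as 1.96 x 4.5 / sqrt(50) = 1.247. At f = 0.50 and S - R = -2.25 the artefact is 0.50 x -2.25 = -1.125, close to that half-width.

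**3. Precision.** With 40 completers per arm (assumed) and SD 4.5, the Follow-Up half-width is 1.96 x 4.5 / sqrt(n): 1.97 with 20 attending (f = 0.50), 2.79 with 10 (f = 0.75) and 4.41 with 4 (f = 0.90).

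**4. Effect of pairing.** If Follow-Up is compared with Visit 12 in the same attenders, the step under no true change is S - S = 0 for every f.

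**5. Reach into the models.** The biomarker model in SAP 9.4 lists Weeks 4 to 72, which leaves Follow-Up out. The FVC and DLCO models contain no such limit.

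**The case against.** The strongest reply is that the reach is small, and much of that is right. The Week 24 primary efficacy endpoint is untouched. The FVC, DLCO and biomarker plots list the first few weeks and then trail off, so Follow-Up is implied there rather than named. For K-BILD, LCQ, SaO2 and FEV1/FVC the SAP already tabulates how many patients have data at each time point, so the fall in numbers would be visible for four of the eight outcomes. The SAP plans no contrast of Week 72 with Follow-Up and makes no withdrawal claim. All visit summaries use observed data, and entry to Part B is itself optional and depends on compliance, so the series already changes composition after Week 24.

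These points limit the importance but do not remove the problem. A falling n shows that patients are missing, not that the missing completers are the ones still on drug. Earlier changes in composition do not coincide with the end of treatment for everyone who remains.

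A reader might go further and infer that Follow-Up will show a false loss, because patients who decline more AP01 are doing worse, and that this would pass as evidence for the drug. The documents do not support that. They say nothing about how non-rollover patients differ, and a false gain or a masked real loss is equally possible. Nor are attenders necessarily people who chose to stop: note 9 to protocol Tables 5 and 6 has patients assessed for AP01-005 eligibility at Visit 12, so some may be ineligible.

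**Conclusion.** The conflict between the SAP and protocol v2.1 is established from the text, and the SAP does not resolve it. As planned, the step from Week 72 to Follow-Up is not interpretable as change after stopping AP01. Its composition part is f x (S - R), with unknown size and sign. Over the assumed ranges it runs from -4.05 to about +2.0 points of FVC % predicted, and it is zero if the two groups do not differ. These figures are illustrations: f, S - R and the Week 72 SD are not in the documents.

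The effect is confined to the Follow-Up summaries, the plots that carry Follow-Up, and the FVC and DLCO models that do not exclude it. It does not touch the Week 24 efficacy result. The correction is still worth making because it is cheap and removes the composition effect by construction.

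**What to change.** 1. Align SAP 3.3, note 1 under Tables 3 and 4, and 3.8.2 with protocol v2.1.
2. Keep Follow-Up in the tables, labelled as off-drug and non-rollover completers only, with the number attending and the number rolled over in each treatment group. Deleting the column is not needed.
3. For each outcome, add the paired within-patient change from Visit 12 to Follow-Up among attenders. It describes those attenders only and, without a control, does not separate stopping drug from 28 days of disease course.
4. Do not join Follow-Up to the on-treatment mean-change lines; show it as a separate point or omit it from the plot.
5. Exclude Follow-Up data from the on-treatment longitudinal models for FVC and DLCO, as the biomarker model already does by stopping at Week 72.

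The cost is minor SAP wording and one extra summary row per outcome. No new data are required.
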